6.4.4 Statin adherence

Statin adherence will be presented with descriptive statistics.

6.4.5 Atorvastatin and metabolites level in patients with failing placebo test for connecting SAMS to atorvastatin and the control group without muscle symptoms

The comparison of levels of atorvastatin and its metabolites between the patients with failing placebo test (non-SAMS) and the patients in the control group (see Figure 1, the study flow chart) will be done with two-sample T tests with adjustment for unequal variances. The mean differences with 95% confidence intervals (based on the t-distribution) and the P-values from the tests will be presented.

6.4.6 Study safety

Study safety will be presented with descriptive statistics.

6.4.7 Muscle symptom location

The difference between atorvastatin and placebo in presence of symptoms locations will be compared between patients with confirmed SAMS (see definition in Section 5.1.2) and non-SAMS patients with the score test for effect in a proportional odds model²² (the Wilcoxon-Mann-Whitney test). The number and percentages of patients in each of the three possible outcome categories (-1, 0, 1) will be presented by SAMS status, together with the P-value from the test.

6.4.8 Muscle symptom characteristics

The difference between atorvastatin and placebo in muscle symptom characteristics will be compared between patients with confirmed SAMS (see definition in Section 5.1.2) and non-SAMS patients with the score test for effect in a proportional odds model²² (the Wilcoxon-Mann-Whitney test). The number and percentages of patients in each of the seven possible outcome categories (-3, -2, -1, 0, 1, 2, 3) will be presented by SAMS status, together with the P-value from the test.

6.4.9 Time to symptoms

Time to symptoms will be presented with descriptive statistics.

6.4.10 Pharmacogenetics

- (i) The mean value of the atorvastatin exposure variable with the highest area under the ROC curve (from the analyses in Section 6.4.3) will be compared between the different genotypes in the genetic variables SLCO1B1, CYP3A5, and CYP3A4 (see Section 5.3.11). The mean (standard deviation) for each genotype will be presented, with a P-value for a test of the null hypothesis of equal means. The two-sample T test with adjustment for unequal variances will be used for CYP3A5 and CYP3A4 (two genotypes) and ANOVA will be used for SLCO1B1 (three genotypes).
- (ii) The frequency of SLCO1B1, CYP3A4, and CYP3A5 genotypes will be compared among patients with confirmed SAMS (see definition in Section 5.1.2), non-SAMS and controls (see Figure 1, the study flow chart) with a Pearson chi-squared mid-P test for unordered r x c tables²¹. The comparisons for CYP3A4/5 will only be performed if there is a statistically significant difference between the genotypes in the atorvastatin exposure variable in (i).

STATISTICAL ANALYSIS PLAN for MUScle Side-Effects of atorvastatin in coronary patients (MUSE) – a randomized controlled trial

6.5 Assumption Checks and Alternative Analyses

The assumption of normally distributed residuals in linear regression and for the two-sample T test will be checked by plotting histograms of the residuals and examining their descriptive statistics, such as mean, median, standard deviation, and coefficient of skewness.

In cases where the distribution of the residuals is deemed to deviate too much from the normal distribution to allow linear regression to be used, a median regression (i.e. a quantile regression) will be performed instead of the linear regression. Then, the median (with a 95% confidence interval and a P-value for the null hypothesis that the median is zero) will be reported instead of the mean. Similarly, if the two-sample T test is deemed to be unsuitable due to too large deviations from the normal distribution, median regression will be used, and differences in medians (with 95% confidence intervals) will be estimated instead of differences in means.

6.6 Missing Data

Due to very close monitoring of adherence to the protocol during the treatment periods, we expect few missing data for the primary outcome and other core self-reported measures. Missing values of VAS-scores in the diary will be replaced by corresponding values from the 1-10 likert scale (Numeric Rating Scale) that were reported simultaneously.

In the unlikely case that there are patients with missing data on both the VAS and NRS scales, those patients will be excluded from the main analyses, but included in a secondary sensitivity analysis (see next section).

6.7 Sensitivity Analyses

- The primary outcome will be analyzed on the per protocol set
- Missing data on the primary outcome will be imputed such that the patient with missing data will have no difference between the two treatment periods in the missing outcome.

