2.3 Sample size

Sample size calculations are based on our being able to detect a 1 cm difference in the VAS symptom score between the treatment periods on atorvastatin and placebo since the smallest change in VAS symptom score corresponding to ‘a little more’ or ‘a little less’ symptoms was 1.3 cm, with a lower limit of the CI at 1 cm in a previous study by Gallagher et al¹⁴. Gallagher et al. report a standard

STATISTICAL ANALYSIS PLAN for MUScle Side-Effects of atorvastatin in coronary patients (MUSE) – a randomized controlled trial

deviation (SD) of 1.7 for a difference of 1.0 between two VAS symptom scores. Because of the differences in both populations and specific VAS scale between that study in this one, we use SD=2.5 to account for a much larger variation in this study. With n=68, we will have 90% power to detect a difference of 1.0, using a one-sample T test. With n=68, we will also have 80% power to detect a difference of 40% SAMS under statins vs. 15% SAMS under placebo, using the McNemar test for paired probabilities. To account for some missing information due to drop-outs or and protocol deviations, we plan to include 80 patients.

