2.4.2 Decision Rule

This trial is designed to address a single primary outcome. Higher SAMS under either atorvastatin treatment or placebo treatment is claimed if the primary null hypothesis is rejected at the 5% (alpha = 0.05) significance level (two-sided).

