6.3 Primary Outcome

The primary outcome, the difference between the VAS symptom scores for atorvastatin and placebo, will be estimated as the predictive overall margin of a linear regression model with the difference (atorvastatin minus placebo) as the dependent variable and the stratification factors in the randomization (i.e. centre and previous statin discontinuation) as covariates. The estimate and its 95% confidence interval will be presented, with a P-value for the null hypothesis that the difference is zero.

The primary analysis will be performed on the full analysis set. A secondary analysis will be performed on the per protocol set.

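### The only missing-data sensitivity analysis (SAP 6.7) imputes a zero difference, which under the planned linear regression leaves the P-value practically unchanged and so cannot test the primary result

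*SAP*

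**What the plan says.** The primary effect "will be estimated as the predictive overall margin of a linear regression model with the difference (atorvastatin minus placebo) as the dependent variable", with centre and previous statin discontinuation as covariates (SAP 6.3). It is reported with a 95% CI and a P-value for a zero difference, on the full analysis set (FAS).

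Section 6.6 substitutes the numeric rating for a missing VAS score. If both are missing, "those patients will be excluded from the main analyses, but included in a secondary sensitivity analysis". Section 6.7 lists two sensitivity analyses. One is that "The primary outcome will be analyzed on the per protocol set", which changes the population and does not deal with missing values. The other imputes a missing primary outcome so that "the patient with missing data will have no difference between the two treatment periods in the missing outcome". No reason is given for choosing zero.

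Three other sections bear on who is imputed:
- Section 5.1.1 uses the last three completed weeks for patients who stop because of intolerable muscle symptoms.
- Section 3.3 limits the FAS to patients with at least three consecutive weeks in each period.
- Section 6.5 replaces linear by median regression if the residuals are too far from normal.

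**The concern.** A missing-data sensitivity analysis should show how far the conclusion depends on what the unseen values might have been. Here each missing difference becomes the null value itself and is then treated as an observation. That lowers the mean, but it also lowers the standard deviation and raises the sample size, so the test statistic has almost nowhere to go.

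What is at stake is how the result will be read. A report that the primary finding was unchanged after imputing missing data would be true almost by construction. It would say nothing about whether missingness was related to symptoms on atorvastatin or on placebo.

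**Working it through.** **Inputs.** From SAP 2.3: SD of the difference 2.5 cm ("we use SD=2.5 to account for a much larger variation in this study"), n = 68, design difference 1.0 cm, 80 enrolled. From 2.4.2: two-sided 5% level. The number imputed, k, is an assumption. The value k = 12 is 80 − 68, the whole allowance for drop-outs and protocol deviations.

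**1. The plan's own figure.** SE = 2.5/√68 = 0.3032, so the noncentrality is 1.0/0.3032 = 3.298 on 67 degrees of freedom. Exact power is 90.2%, and 68 is the smallest n reaching 90%. The stated 90% is reproduced.

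**2. Why zeros leave the test almost unchanged.** For differences d in N patients, let q = (Σd)²/Σd². The one-sample statistic satisfies t² = q(N − 1)/(N − q). Adding zeros changes neither sum, so q is fixed and only N changes.

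At an observed mean of 0.61:
- Σd = 68 × 0.61 = 41.48
- Σd² = 67 × 2.5² + 68 × 0.61² = 418.75 + 25.30 = 444.05
- q = 41.48²/444.05 = 3.875
- N = 68: t² = 3.875 × 67/64.125 = 4.048, t = 2.012
- N = 80: t² = 3.875 × 79/76.125 = 4.021, t = 2.005

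**3. Results with n = 68 observed and SD 2.5.**

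| Observed mean (cm) | Zeros added | Estimate | SD | t | P | 95% CI width |
|---|---|---|---|---|---|---|
| 0.50 | 0 | 0.50 | 2.50 | 1.649 | 0.104 | 1.21 |
| 0.50 | 12 | 0.43 | 2.31 | 1.646 | 0.104 | 1.03 |
| 0.61 | 0 | 0.61 | 2.50 | 2.012 | 0.0482 | 1.21 |
| 0.61 | 12 | 0.52 | 2.31 | 2.005 | 0.0484 | 1.03 |
| 1.00 | 0 | 1.00 | 2.50 | 3.298 | 0.00156 | 1.21 |
| 1.00 | 12 | 0.85 | 2.33 | 3.263 | 0.00163 | 1.04 |

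The estimate shrinks by n/(n + k), here 68/80 = 0.85. Even with 68 zeros, as many as there are real observations, P at the design effect is only about 0.0018.

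**4. The planned model with covariates.** The overall margin with two binary covariates was simulated with 12 of 80 imputed, 1,500 trials per scenario. The significance verdict changed in under 0.3% of trials, and the median change in P was below 0.001.

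**5. Other imputed values do move P.** With 12 imputed and an observed mean of 0.61, P is 0.169 if each missing difference is set to −1 cm, 0.048 at 0 and 0.011 at +1 cm. At an observed mean of 0.76 (t = 2.5), significance is lost when each is set to about −0.78 cm. At the design effect the corresponding value is about −1.91 cm. These imputed values are illustrative.

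**6. Informative loss (assumed mechanisms, true mean 1.0, 12 of 80 lost).**
- Loss mainly among large positive differences: complete cases estimate 0.43 and zero imputation 0.37. Rejection is 39.1% and 39.0%, against 94.6% with full data.
- Loss mainly among large negative differences: complete cases estimate 1.58 and zero imputation 1.34.

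In neither case does the zero-imputed test differ from the complete-case test in a way that would warn the reader.

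**7. Median-regression fallback.** In 300 simulated trials with mean 0.75, adding 12 zeros moved the median from 0.72 to 0.28 and rejection from 35% to 14%. The near-invariance belongs to the mean model only.

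**The case against.** The best defence is that little data should be missing. The numeric rating backs up the VAS, patients are telephoned weekly, and 6.6 calls the loss of both scales unlikely. Twelve is an upper figure that also covers protocol deviations, many of which would not lead to imputation. With two missing and an observed mean of 0.50 cm, the estimate moves only to 68 × 0.50/70 = 0.486 cm. This stands. It limits the impact but does not make the check informative.

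Four stronger readings are tempting, and the SAP does not support them:

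- *Patients who stop atorvastatin for intolerable symptoms are scored as having no effect.* Those with at least three weeks in each period keep observed scores (5.1.1). Those with less in either period are outside the FAS (3.3), and the SAP does not say whether randomised patients outside the FAS are imputed.
- *Zero imputation moves the estimate away from the truth.* That depends on who is lost. In step 6 it does so under one mechanism and moves towards the truth under the other (1.58 to 1.34, truth 1.00).
- *The check can reveal nothing at all.* The estimate and CI do change, and under the 6.5 fallback so does the test.
- *The understated variance creates false significance.* It does not, because the estimate falls with the SD. What remains is an interval that looks more precise as data are lost.

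**Conclusion.** The point holds in a limited form. Under the planned linear regression, zero imputation cannot test the robustness of the primary P-value. With the plan's SD and sample size and 12 patients imputed, P changes by about 0.0002 or less in the three cases tabulated, while the estimate shrinks by 15% and the interval narrows by about 15%. It allows for informative missingness in neither direction, and its population (FAS or all randomised) is not fixed.

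The figures assume SD 2.5 cm and up to 12 missing differences. The algebra in step 2 is for the one-sample test, and the simulation in step 4 supports it for the covariate-adjusted model. No direction of bias is established, because the SAP does not tell us why data would be missing. This is a worthwhile, inexpensive improvement to a secondary analysis. It is not a fault in the primary analysis.

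**What to change.** Replace the zero imputation in 6.7 with a tipping-point (delta-adjusted) analysis:

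1. State the population: all randomised patients with at least one scored period. Report separately how many have none.
2. Multiply impute the missing period score.
3. Shift missing atorvastatin scores and missing placebo scores separately, over a range with negative and positive values, for example −4 to +4 cm. Upward shifts of atorvastatin scores alone would not be enough. They can only raise the atorvastatin-minus-placebo difference, so they could never overturn a significant excess on atorvastatin.
4. Report the shift at which the conclusion changes, or that none in the range changes it.

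A mixed model on the two period scores may be added as a missing-at-random reference. It does not by itself address informative stopping.

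The cost is SAP wording, a little more programming and a sensitivity interval that will be wider than under zero imputation. If few data are missing, the analysis will simply show that the result is insensitive to them.

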6.8 Subgroup Analyses

There will be no subgroup analyses; however, some of the secondary outcomes are defined in subsets of the trial sample, or involve comparisons of groups defined by the SAMS classification:

- The analyses in Section 6.4.6 only include non-SAMS patients (and patients in the control group)
- The analyses in Section 6.4.8 compare patients with confirmed SAMS with non-SAMS patients
- The analyses in Section 6.4.9 compare patients with confirmed SAMS with non-SAMS patients
- The analysis of time to confirmed SAMS in Section 6.4.10 only includes patients with confirmed SAMS

7 Safety Analyses

Safety endpoints will be under the responsibility of the primary investigators at the participating centres and will be collected:

STATISTICAL ANALYSIS PLAN for MUScle Side-Effects of atorvastatin in coronary patients (MUSE) – a randomized controlled trial

- Every 7th days: direct telephone contact with the patient for assessment of intolerable muscle symptoms and symptoms of unstable CHD (i.e. new-onset angina pectoris and/or dyspnoea) after a standardized protocol by a specially trained study nurse.
- Blood samples collected for analyses of ALAT and CK at the end of each 7 weeks treatment period or if intolerable muscle symptoms were reported by the patients.
- Continuous surveillance of serious adverse events (SAEs) obtained through direct weekly telephone contact with the patients and through continuous monitoring of hospital admissions during the study period.

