3.3 Analysis Populations

The Enrolled set will include all patients who have provided informed consent and have been included into the study data base.

The Full Analysis Set (FAS) will be defined as all patients randomly assigned to a treatment group having completed at least three consecutive study weeks on each treatment period.

The Safety Analysis Set will include all patients having received at least one study treatment tablet after randomisation.

The Per Protocol Analysis Set (PPS) will include all randomised patients meeting the study eligibility criteria and with no major protocol deviations affecting the treatment efficacy (i.e. <10% missing data* in the patient diary and >80% tablet adherence in the drug and placebo period, separately), and also being classified as non-adherent to atorvastatin in the end of the placebo study period by direct blood

STATISTICAL ANALYSIS PLAN for MUScle Side-Effects of atorvastatin in coronary patients (MUSE) – a randomized controlled trial

sample measurement according to Kristiansen et al.¹⁵. Patients being classified as partial adherent or non-adherent to atorvastatin therapy in the end of the atorvastatin study period by direct blood sample measurement (Kristiansen et al.¹⁵) will be excluded from the data analyses concerning blood levels of parent drug and metabolites.

**The percentage of missing data for the core self-reported variables in the diary (i.e. the VAS 0-10 cm likert scale and the 0-10 numeric rating scale) will be reported.*

4 Trial Population

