5.3.6 Study safety

- Proportion of patients with new-onset CHD symptoms (e.g. angina, dyspnoea)
- Intolerable muscle symptoms leading to discontinuation from the treatment arm
- Proportion of patients with creatine kinase (CK) > 10 times upper limit of the normal range or alaninaminotransferase (ALT) > 3 times upper limit of the normal range in blood

STATISTICAL ANALYSIS PLAN for MUScle Side-Effects of atorvastatin in coronary patients (MUSE) – a randomized controlled trial

- Proportion of patients with serious adverse events (SAEs) and Suspected Unexpected Serious Adverse Reactions (SUSARS).

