6.4 Secondary Outcomes

All secondary outcomes will be analysed on the FAS, except where noted otherwise.

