7.1 Adverse Events

As outlined in Section 6.4.7, adverse events will be presented with descriptive statistics.

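### The SAP gives three conflicting populations for the safety analysis: a misnumbered restriction in 6.8, the FAS default in 6.4, and a Safety Analysis Set in 3.3 that no safety section invokes

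*SAP*

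**What the plan says.** Four places in the SAP bear on who enters the safety tables.

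- Section 6.8, listing secondary analyses that use subsets or compare SAMS groups: "The analyses in Section 6.4.6 only include non-SAMS patients (and patients in the control group".
- Section 6.4.6, headed Study safety, in full: "Study safety will be presented with descriptive statistics". It names no population.
- Section 6.4, which opens the secondary analyses: "All secondary outcomes will be analysed on the FAS, except where noted otherwise". Study safety is one of these outcomes (5.3.6). Section 3.3 limits the FAS to randomised patients who completed at least three consecutive weeks in each treatment period.
- Section 3.3: "The Safety Analysis Set will include all patients having received at least one study treatment tablet after randomisation".

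The outcomes in 5.3.6 carry no SAMS condition; the first reads "Proportion of patients with new-onset CHD symptoms (e.g. angina, dyspnoea". The list also includes discontinuation for intolerable muscle symptoms. Section 7.1 refers back for its method: "As outlined in Section 6.4.7, adverse events will be presented with descriptive statistics". Section 6.4.7 is the analysis of muscle symptom location.

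**The concern.** Confirmed SAMS is defined in 1.2.2 and 5.1.2 by higher symptom scores on atorvastatin than on placebo. A safety table without those patients would be selected on the trial's primary outcome variable, in a trial about muscle side-effects.

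The FAS default has a similar effect by another route. A patient who stops before three weeks in either period is outside the FAS, and 3.2.2 foresees such patients by listing early discontinuation as a major protocol deviation. If the stop was for intolerable muscle symptoms, a safety event named in 5.3.6 would go uncounted because it came early.

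The one set suited to safety reporting is defined in 3.3 and then not used. An analyst working from the text would have to choose between populations, and the plan should not leave that choice open.

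**Working it through.** No arithmetic applies. The check compares each cross-reference with the section it points to, and then asks which population the text assigns to safety.

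**Step 1: cross-references.**

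| Where | Number printed | What that section holds | Section that fits |
|---|---|---|---|
| 6.8, first item | 6.4.6 | Study safety, descriptive, no subset | 6.4.5 |
| 6.8, second item | 6.4.8 | Symptom characteristics, confirmed SAMS vs non-SAMS | 6.4.7 |
| 6.8, third item | 6.4.9 | Time to symptoms, descriptive only | 6.4.8 |
| 6.8, fourth item | 6.4.10 | Pharmacogenetics | 6.4.9 |
| 7.1 | 6.4.7 | Symptom location | 6.4.6 |
| 6.4.10 | 5.3.11 | Does not exist; 5.3 ends at 5.3.10 | 5.3.10 |

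The first item fits 6.4.5 because that section compares metabolite levels "between the patients with failing placebo test (non-SAMS) and the patients in the control group". The third item, "The analyses in Section 6.4.9 compare patients with confirmed SAMS with non-SAMS patients", cannot describe a section that contains only descriptive statistics. The second item happens to be true as printed, because 6.4.7 and 6.4.8 both compare confirmed SAMS with non-SAMS. Lowering all six numbers by one matches every statement to its section.

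**Step 2: the population for safety under each passage.**

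| Source | Population for 6.4.6 | Who is left out |
|---|---|---|
| 6.8 as printed | Non-SAMS patients and controls | Confirmed-SAMS patients |
| 6.4 default | FAS | Anyone without three consecutive weeks in each period |
| 3.3 Safety Analysis Set | At least one tablet after randomisation | No treated randomised patient |

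The 6.8 wording also brings in the control group. Section 2.1 describes the controls as consecutively included and treated open-label, so they are not randomised and fall outside the Safety Analysis Set as 3.3 words it.

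**Step 3: which passage governs.** The 6.4 default yields only to an exception noted elsewhere. Sections 5.3.6, 6.4.6, 7 and 7.1 do not mention the Safety Analysis Set. The only later passage that attaches a population to 6.4.6 by number is the misdirected item in 6.8. Once that item is corrected to 6.4.5, the FAS default still stands for safety.

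**The case against.** The strongest reply is that this is a numbering slip that gives itself away. The shift is uniform, and only 6.4.5 compares non-SAMS patients with controls. The fourth item names time to confirmed SAMS, which cannot be pharmacogenetics. Section 6.8 opens by saying there are no subgroup analyses and only summarises restrictions set elsewhere. A Safety Analysis Set without any SAMS condition exists in 3.3. Section 7.1 states its method in its own sentence, so the wrong pointer there costs little.

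Most of this stands. A reader might infer from 6.8 that the plan means to remove confirmed-SAMS patients from safety reporting. The document does not support that: 3.3, 5.3.6, 6.4.6 and section 7 contain no such restriction, and the pattern of errors points to stale numbering. Nor does 6.4.7 lose its comparison rule, since it states the confirmed-SAMS versus non-SAMS comparison in its own text.

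A reader might also try to size the effect by applying the 36% in 1.1 or the 40% in 2.3 to the 80 planned patients. Neither rate serves. The 36% comes from simvastatin 20 mg in subjects without cardiovascular disease, under a different criterion. The 40% is the assumed rate of SAMS under statin, set against 15% under placebo, and not a rate of confirmed SAMS. Section 6.4.1 also takes the confirmed-SAMS proportion over the FAS and not over all randomised patients. An argument that raised creatine kinase would be hidden is weak too, because 1.1 says SAMS usually occurs with normal or minimally elevated levels.

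The reply does not answer the FAS default. Defining a safety set in 3.3 does not assign it to an analysis, and 6.4 assigns a different set to all secondary outcomes.

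**Conclusion.** The point holds as a contradiction in the written safety population. It is not evidence of an intended exclusion. Section 6.8 as printed would omit confirmed-SAMS patients, and 6.4 as printed would omit early stoppers. Section 3.3 would omit no treated randomised patient but is not linked to the analysis. The evident intent is to report all treated patients, and a careful analyst would probably see through 6.8. The FAS default is less obvious and would survive a correction of the numbers alone.

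The number of patients affected cannot be derived: the SAP gives no usable confirmed-SAMS rate and no expected rate of stopping before three weeks. The conclusion rests on reading 6.4 as covering safety, which follows from safety being listed among the secondary outcomes in 5.3.6 and analysed in 6.4.6. The change should be made because the error is certain and the repair is small.

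**What to change.** - In 6.8, change the four references to 6.4.5, 6.4.7, 6.4.8 and 6.4.9, in that order.
- In 7.1, change the reference to 6.4.6.
- In 6.4.10, change the reference to 5.3.10.
- In 6.4.6, state that safety is summarised on the Safety Analysis Set, meaning all treated randomised patients whatever their SAMS classification, as an explicit exception to the FAS default in 6.4, and that any control-group safety data are shown separately.

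The cost is six section numbers and one statement in the SAP. No data collection, sample size or primary analysis changes.
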